6. SUPPORTING DOCUMENTATION

6.1. Appendix 1 List of Abbreviations

| | |
|-----------|--|
| ADaM | Analysis Data Model |
| AE | adverse event |
| AESI | adverse event of special interest |
| ALT/SGPT | alanine aminotransferase |
| AST/SGOT | aspartate aminotransferase |
| BL | baseline |
| BMI | body mass index |
| BUN | Blood Urea Nitrogen |
| CDDM | Clinical Development Data Management |
| CEC | Critical Event Committee |
| CLs | confidence limits |
| COVID-19 | Coronavirus Disease 2019 |
| CRF | case report form |
| CSR | Clinical Study Report |
| DPS | Data Presentation Specifications |
| DSUR | Development Safety Update Report |
| EAIR | exposure-adjusted incidence rate |
| ECG | electrocardiogram |
| eCRF | electronic case report form |
| EOS | End of Study |
| EOT | End of Treatment |
| ERA | endothelin-receptor antagonist |
| FDA | Food and Drug Administration |
| HGR/HGRAO | Human Genetic Resources/ Human Genetic Resources Administration Office |
| HPAH | Heritable Pulmonary Arterial Hypertension |
| IB | Investigator Brochure |
| ICE | Integrated Computer Environment |
| IMTD | Individual Maximum Tolerated Dose |
| INR | International Normalized Ratio |
| IPAH | Idiopathic Pulmonary Arterial Hypertension |
| IQ | interquartile |
| KM | Kaplan Meier |
| MAA | Marketing Authorization Application |
| MACE | Major adverse cardiovascular events |
| MedDRA | Medical Dictionary for Regulatory Activities |
| NDA | New Drug Application |
| NT-proBNP | N-terminal prohormone of brain natriuretic peptide |
| OLE | AC-065A303/GRIPHON OL |
| OLS | Treated Set – OL |
| OSB | Ophthalmology safety board |
| PAH | Pulmonary Arterial Hypertension |
| PBRER | Periodic Benefit-Risk Evaluation Report |
| PDs | Protocol Deviation |
| PDE5-I | phosphodiesterase type 5 inhibitor |
| PT | Preferred term |
| RDB | AC065A302/GRIPHON - Randomized Double Blind |
| RMP | risk management plan |
| SAE | serious adverse event |
| SAP | Statistical Analysis Plan |
| SAS | Statistical Analysis Software |
| SCS | Summary of Clinical Safety |
| SD | standard deviation |
| SDG | Standard Definition Group |
| sGC | Soluble guanylate cyclase |

| | |
|---------|--|
| SDTM | Study Data Tabulation Model |
| SOC | System Organ Class |
| SOP | Standard Operating Procedure |
| STS | Selexipag Treated Set |
| TE-AEs | treatment-emergent adverse event |
| TE-SAEs | treatment-emergent serious adverse event |
| ULN | upper limit normal |
| WHO FC | World Health Organization Functional Class |
| WHO-DD | World Health Organization Drug Dictionary |
| 6MWD | Six Minute Walk Distance |

6.2. Appendix 2 Changes to Protocol-Planned Analyses

Analysis of Exposure (Sections 5.5.1 and 5.5.1.1) by IMTD is included. Reason: The definition and analysis are in line with the original NDA/MAA submission in 2014 as well as supplemental NDA/MAA submission for long-term safety and survival in 2020, and the RMP version 8.1 support to 5-year MAA renewal. In both submission dossiers, the A303 data were already pooled with A302.

To prevent a violation of China's Human Genetic Resources (HGR) regulation, data participants in China for A303 that were due beyond 20 December 2019 are either not collected in clinical database or will be excluded from SDTM.

Protocol deviations (PDs) (Section 6.4) include also COVID-19 and HGRAO (Chinese HA) related PDs.

6.3. Appendix 3 Demographics and Baseline Characteristics

Table 9 lists the demographic variables that will be summarized.

Table 9: Demographic Variables

| Continuous Variables | Summary Type |
|---|--|
| ^Age (years) | Descriptive statistics (N, mean, standard deviation [SD], median and range [minimum and maximum], and IQ range). |
| ^Weight (kg) | |
| Height (cm) | |
| ^Body Mass Index (BMI) (kg/m ²) | |
| ^6MWD (m) | |
| ^NT-proBNP (ng/L) | |
| ^Time since diagnosis (years) | |
| Categorical Variables | Frequency distribution with the number and percentage of participants in each category. |
| ^Age (<18 years, 18-64 years, 65-74 years, 75-84 years, and ≥85 years) | |
| Sex (male, female) | |
| Race/ethnicity (Caucasian /Hispanic, Asian, Black, Other) | |
| Geographical regions (Asia, Eastern Europe, Western Europe + Australia, North America, Latin America) | |
| ^BMI (underweight <18.5 kg/m ² , normal 18.5-<25 kg/m ² , overweight 25-<30 kg/m ² , obese ≥30 kg/m ²) | |
| Etiology (Idiopathic (IPAH), Heritable (HPAH), Drug or Toxin Induced, Assoc. with Connective Tissue Disease, Assoc. with Congenital Heart Disease, Associated with HIV Infection) | |
| ^WHO-FC (I, II, III, and IV) | |
| ^Concomitant PAH medication at BL (None, ERA alone, PDE5i alone, ERA+ PDE5i)* | |
| ^NT-proBNP (low <300 ng/L, medium 300 =< - =< 1400 ng/L, high > 1400ng/L) | |
| ^Number of low-risk criteria met at baseline (0, 1, 2, 3)** | |
| ^Antithrombotic medication at baseline | |

^a If multiple race categories are indicated, the Race is recorded as 'Other'.

*Details of PAH medication at baseline are presented in Section 6.5.

**Low risk criteria met at baseline are: NT-proBNP < 300 ng/L, WHO functional class equal to I/II, 6MWD > 440m.

^For both STS (A302+A303) and OLS, these variables should be re-baselined according to Section 5.1.5.

Some baseline characteristics (specified with symbol ^ in Table 9 above) should be re-baselined according to the analysis set used: for STS (A302+A303), baseline covariates were assessed prior to the start of selexipag; for OLS they were assessed prior to the start of selexipag in A303 (Section 5.1.5). Especially for age, the following formula will be used: age in years at A302 screening date – year of A302 screening date + year of A303 start of intervention.

Demographic variables will be summarized separately for STS and OLS. For OLS, they will be summarized showing all treatment sequences:

| | Treated Set - OL (A303) ^ | | | | | |
|--|---------------------------|------------|-------------------|------------|-------------------|------------|
| | Ex-Selexipag 330 | | Ex-placebo 379 | | Total A303 709 | |
| | BL at A302 | BL at A303 | BL at A302 | BL at A303 | BL at A302 | BL at A303 |
| | | | | | | |

^Participants treated in A303.

Separate listings of demographic variables for STS and OLS will also be produced.

6.4. Appendix 4 Protocol Deviations

PDs are defined in the following document: TV-eFRM-06818.

PDs are listed and summarized displaying counts and percentages of participants with at least one PD. A similar table is presented for major PDs. Only data of OLS (A303) will be summarized.

The PDs in the summary tables will be sorted by overall frequency, in descending order; if a tie occurs, the tied characteristics will be sorted alphabetically.

All reported PDs will be described in a participant's listing. Major PDs will be flagged accordingly.

Protocol deviations related to COVID-19 will be summarized for all such PDs and for major such PDs on OLS and also be presented in a listing.

6.5. Appendix 5 Prior and Concomitant Medications

Prior and Concomitant medications will be coded using the World Health Organization Drug Dictionary (WHO-DD). These medications are recorded on the ‘Previous/Concomitant Medication’ pages of the A302 and A303 CRF. Prior medications are defined as any therapy used before the day of the first dose of study intervention. Concomitant medications at baseline are defined as any therapy started on the same day as the first dose of study intervention, or before and continued after the first dose of study intervention. Concomitant medications started during intervention are defined as any therapy started after the day of the first dose of study intervention (excluding medication started after the end of study intervention). Handling missing data is defined in Section 6.5.1.

For A302 general prior medications and concomitant medications were already reported in the A302 CSR. General concomitant medications in A303 are not of interest and will not be summarized. Only listings of all concomitant medications at baseline or started during study intervention will be generated separately for OLSs and STS (A302+A303).

Concomitant PAH-specific medications will be summarized by ingredient name and PAH-specific medication group name (Table 10) using grouping 1 and 2 as defined in Section 5.6.8. For each of the following 2 types of concomitant PAH-specific medications, summary of OLS and STS (A302+A303) will be presented in the same table according to Section 4.

- Concomitant PAH-specific medications at baseline, i.e., any therapy used on the same day as the first dose of study intervention and might continue after the first dose of study intervention). For the STS (A302+A303), baseline refers to the first dose of selexipag either in A302 (participants who received selexipag in A302) or in A303 (participants who received placebo in A302).
- Concomitant PAH-specific medications started during study intervention.

Listings of PAH specific concomitant medications at baseline or started during study intervention will be generated separately for OLS and STS (A302+A303).

Additionally, the following will be summarized separately for OLS and STS (A302 + A303):

- Number of participants who added a post-baseline new class of PAH-specific medication. A post-baseline new class of PAH-specific medication is defined as any new class of PAH therapy (i.e., ERA/PDE5-i/sCG stimulator/Prostacyclin and analogs only; ERA+PDE5-i; ERA+sCG stimulator; ERA+Prostacyclin and analogs, PDE5-i+sCG stimulator, sCG stimulator+Prostacyclin and analogs, etc.) started after baseline (see Section 5.1.5 for the definition of baseline for STS and OLS).
- Duration of exposure in years (i.e., sum of total exposure duration and mean) before, after and without adding a post-baseline new class of PAH-specific medication.
- Duration of exposure before and after adding a new class of PAH therapy will be given for participants who added at least 1 post-baseline new class of PAH therapy. Exposure duration before adding a new class of PAH therapy will be computed as (start of new class of PAH therapy - start of treatment) / 365.25; Exposure duration after adding a new class of PAH

therapy will be derived as (end of treatment - start of new class of PAH therapy+1) / 365.25. Duration of exposure without addition of a new class of PAH therapy will be given for the number of participants with (or without) concomitant PAH therapy at baseline minus the number of participants who added at least 1 post-baseline new class of PAH therapy, and will be computed as (end of treatment - start of treatment+1) / 365.25.

Table 10: PAH Specific Therapies

| Group name for the Analysis outputs | Category | Subcategory | Generic names |
|---|---|-----------------|---|
| ERA | Antihypertensives for pulmonary arterial hypertension | ERA | ambrisentan, bosentan, sitaxentan, macitentan |
| PDE5-i | | PDE-5 Inhibitor | sildenafil, tadalafil, vardenafil, udenafil |
| sCG stimulator | | sGC stimulator | riociguat |
| Prostacyclin/prostacyclin agonists | Prostanoids | | epoprostenol, treprostinil, iloprost, beraprost |
| Categories are identified by searching the coded WHODRUG preferred terms for occurrence of any of the ingredient names. E.g., 'Sildenafil' and 'Sildenafil Citrate' will both be assigned to sildenafil and thus both considered as PDE-5 inhibitors. | | | |

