3.2.3 Exclusion criteria

1. Pediatric patients (i.e., < 18 years of age).
2. Patients who are not able to perform Visit 1 of AC-065A303/GRIPHON OL within 2 weeks (i.e., 14 days) of the last visit in AC-065A302/GRIPHON.
3. Patients who have started receiving prostacyclin (epoprostenol) or prostacyclin analogs (i.e., treprostinil, iloprost, beraprost) since the last study drug intake in AC-065A302/GRIPHON⁴.
4. Severe hepatic impairment (Child-Pugh C)
5. Females who are pregnant or who plan to become pregnant during the study or are breast-feeding.
6. Any known factor or disease that might interfere with treatment compliance, study conduct or interpretation of the results, such as drug or alcohol dependence, or psychiatric disease.
7. Known hypersensitivity to selexipag or any of the excipients.

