3.2.4 Concomitant medications

3.2.4.1 Allowed concomitant medications

PAH-specific therapies including ERAs, PDE-5 inhibitors, and/or riociguat.

Concomitant use of inhaled, i.v., and s.c. prostacyclin and prostacyclin analogs (e.g., epoprostenol, treprostinil, iloprost) is permitted, as deemed medically indicated by the

³ A woman is considered to have childbearing potential unless she meets at least one of the following criteria:

- previous bilateral salpingo-oophorectomy or hysterectomy
- premature ovarian failure confirmed by a specialist gynecologist
- pre-pubescence, XY genotype, Turner syndrome, uterine agenesis
- age > 50 years with amenorrhea for at least 24 consecutive months prior to screening

⁴ Single administration of i.v./inhaled prostacyclin or analogs used for acute vasodilator testing during a RHC procedure is allowed.

investigator, to stabilize a patient with worsening of PAH or to switch a patient to i.v. or s.c. treatment.

If a patient is scheduled for an intervention that may temporarily prevent him/her from taking oral medications, it is allowed to interrupt selexipag treatment and temporarily switch to another IP receptor agonist medication with a more convenient route of administration with regard to the patient's medical condition. The patient will be allowed to restart selexipag once he/she can take oral medications again. When re-starting selexipag, it is recommended to begin with the lowest dose (i.e., 1 tablet/200µg b.i.d.) and to progressively increase the selexipag dose to reach the maximum dose that was previously tolerated by the patient. The decrease of the other IP receptor agonist dose will be done in parallel with the increase of selexipag dose based on patient's individual tolerability. If the patient experiences pharmacological side effects that cannot be tolerated while he/she is concomitantly taking selexipag and the other IP receptor agonist medication, a dose reduction or stop of this other IP receptor agonist will be considered before considering a dose reduction or a stop of selexipag.

Single administration of i.v./inhaled prostacyclin or analogs used for acute vasodilator testing during a right heart catheterization (RHC) procedure is allowed.

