3.9.2.2 Concomitant medications

All concomitant medications (ongoing, initiated, discontinued) including PAH specific medications and diuretics taken in the period between Visit 1 and up to EOS will be recorded on the Concomitant Medication pages of the CRF. Any dose changes in PAH specific medications (e.g., ERAs, PDE-5 inhibitors, riociguat, prostacyclin, prostacyclin analogs, and initiation of continuous chronic oxygen therapy) must be recorded in the CRF.

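### Does a single vasodilator-test dose of prostacyclin distort the SAP's count of participants who added a new PAH drug class?

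*SAP*

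**What the plan says.** SAP section 6.5 plans, separately for the open-label set (OLS) and the selexipag-treated set (STS), a count of participants who added a PAH class after baseline, and a split of exposure into time before, after and without such an addition. The rule is: "A post-baseline new class of PAH-specific medication is defined as any new class of PAH therapy". Prostacyclin and its analogs form one class. On identification, Table 10 states: "Categories are identified by searching the coded WHODRUG preferred terms for occurrence of any of the ingredient names". The prostacyclin row lists epoprostenol, treprostinil, iloprost and beraprost.

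For participants who added a class, exposure before the addition is "computed as (start of new class of PAH therapy - start of treatment) / 365.25". Exposure after it runs to the end of selexipag treatment, not to the end of the added drug: "therapy will be derived as (end of treatment - start of new class of PAH therapy+1) / 365.25".

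Protocol section 3.2.4.1 states: "Single administration of i.v./inhaled prostacyclin or analogs used for acute vasodilator testing during a right heart catheterization (RHC) procedure is allowed". Section 3.9.2.2 covers all concomitant drugs, "including PAH specific medications and diuretics taken in the period between Visit 1 and up to EOS will be recorded". Exclusion criterion 3 bars "Patients who have started receiving prostacyclin (epoprostenol) or prostacyclin analogs (i.e., treprostinil, iloprost, beraprost) since the last study drug intake" of the double-blind study, and its footnote adds: "Single administration of i.v./inhaled prostacyclin or analogs used for acute vasodilator testing during a RHC procedure is allowed".

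**The concern.** The protocol appears to separate a diagnostic dose from treatment. It exempts the dose from the exclusion criterion on starting prostacyclin, and section 3.2.4.1 permits it in a paragraph apart from prostacyclin given to stabilize or switch a patient. The SAP draws no such line: sections 6.5, 6.5.1 and 5.6.8 and Table 10 contain no condition on purpose, number of doses or duration.

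A post-baseline test dose of a Table 10 agent would therefore be classified like a lasting addition of prostacyclin therapy. All exposure from that date would be labelled as following the addition, although the participant took the drug for one day. If a true start came later, the test dose would also make the class start date too early. At stake is whether the tables overstate how many participants needed more PAH therapy and understate selexipag exposure without it.

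**Working it through.** **1. Does the rule catch the dose?** Protocol 3.9.2.2 has no carve-out for a test dose, so it should be in the CRF. The Table 10 search finds the ingredient name, and the start date is after baseline. It counts, provided that the agent is in Table 10 and the class was not in use at baseline. Beraprost drops out in practice: the permitted test dose is intravenous or inhaled, and protocol 3.2.4.2 lists beraprost among the prohibited oral agonists.

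**2. Effect on one participant.** Let treatment start on Day 1, the test dose fall on Day d, and treatment end on Day T. The SAP formulas give:

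- before = (d − 1)/365.25
- after = (T − d + 1)/365.25
- before + after = T/365.25, for every d

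T/365.25 is what the participant would otherwise contribute to 'without'. Person-time is moved between categories, not lost. Actual use is 1/365.25 = 0.003 years.

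The documents give no individual dates. For illustration, assume treatment began at enrolment and was ongoing on 1 September 2019, the interim cut-off in the SAP introduction. Enrolment ran from 7 July 2010 to 2 September 2014 (SAP 1.2).

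| T (days) | T (years) | d | Before (years) | After (years) |
|---|---|---|---|---|
| 1826 (last enrolment) | 5.00 | 2 | 0.003 | 4.997 |
| 1826 | 5.00 | 914 | 2.50 | 2.50 |
| 1826 | 5.00 | 1826 | 4.997 | 0.003 |
| 3344 (first enrolment) | 9.16 | 2 | 0.003 | 9.153 |

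If a test on an assumed Day 366 is followed by a true start on Day 731, then 365/365.25 = 1.00 year moves from 'before' to 'after', and the count does not change.

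**3. Effect on the group.** SAP section 4 gives 709 participants in OLS and 953 in STS. One case is 1/709 = 0.14 points or 1/953 = 0.10 points. The number of cases is not in the documents. If 0.5% to 5% were affected, that would be about 4 to 35 participants in OLS and 5 to 48 in STS. These percentages are assumptions, and zero is also possible: no right heart catheterization appears in the protocol's section 3.10 visit descriptions or in Table 2.

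**4. Which outputs use the variable?** Only the new-class count and the exposure split. The PAH-medication subgroups for adverse events, deaths and laboratory abnormalities (SAP 5.6.8) are defined at baseline. The survival analysis (5.5.2.4.1) does not use added therapy. The summary of PAH-specific medications started during treatment (6.5) would also show the dose, but there it reports truthfully what was given.

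**5. Is there a contradiction with the protocol?** The footnote qualifies an eligibility criterion covering the interval since the last dose in the double-blind study. It defines no analysis variable. The two documents serve different purposes here and do not conflict.

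**The case for a change.** The best case for a change is that the split exists to show how much selexipag exposure accrued with and without added PAH therapy, and a diagnostic dose is not added therapy. One can reply that the SAP's words, PAH therapy, already exclude it, but a name search gives the programmer no means of applying that reading. Nothing in the two outputs would reveal the misclassification, and a sentence in 6.5 costs little. As a reading of the text, all of this stands.

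The gain from a written exception is doubtful. The available marker, equal start and stop dates, is a proxy for purpose, so a genuine one-day stabilizing course would leave the count as well. Any such rule must also fit section 6.5.1, under which a missing start date already places the medication before treatment, and some partial dates are set to the treatment start. More basically, the SAP runs 'after' from the first addition to the end of treatment for every class, however briefly the drug is used. The temporary switch to another IP receptor agonist and the short stabilizing use that protocol 3.2.4.1 allows fall under the same convention. An exception for test doses alone would leave those cases as they are, and the new-class count would then need a footnote to reconcile it with the summary of medications started during treatment.

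**Conclusion.** The literal reading holds, but no change is needed. The SAP splits exposure at the first record of a new class and is silent on one rare diagnostic use. Each affected participant adds 0.14 points (OLS) or 0.10 points (STS) to a descriptive percentage and moves his or her own treatment time out of 'without'. That shift makes exposure without added therapy look smaller, so it does not flatter selexipag. No hypothesis is tested, and no safety or survival result depends on the variable.

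Section 6.5 already provides listings of PAH-specific medications for both sets, so an analyst who finds a test dose can identify it and footnote it. The data presentation specifications named in the SAP version history may already settle the point; they were not available.

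This rests on test doses being uncommon, which the absence of a scheduled catheterization suggests but does not prove. Even at the assumed 5%, the effect would be about five points on the added-class percentage and nothing elsewhere. The treatment durations shown use an interim cut-off and the open-label enrolment dates, so they do not describe final exposure or selexipag time in the double-blind study. Whether test doses were permitted and recorded in that study depends on its own protocol, which was not available.

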6.5.1. Imputation Rules for Missing Start/End Date of Concomitant Medication

Incomplete and missing start dates of medication in A302/A303 will be imputed as follows:

- If the end date of the medication is not before the start of study intervention and if the study intervention start falls in the range of possible dates, the start date of the medication is imputed with the study intervention start date. In all the other cases, the start date of the medication is imputed with the lower limit.
- If the start date of the medication is missing, the medication is considered to have started before start of study intervention.

Incomplete and missing end dates of medication in A302/A303 will be imputed as follows:

- If the end date is incomplete, the upper limit is used.
- If the end date is missing: no imputation, the medication is considered ONGOING.

6.6. Appendix 6 Medical History

Not applicable.

